4.1 Description of Investigational Product

Technegas is a structured ultra-fine dispersion of Technetium-99m (Tc-99m) labeled carbon particles produced by a TechnegasPlus Generator. Technetium-99m labeled carbon aerosol, delivered from the TechnegasPlus Generator system, distributes to normally ventilated regions of the lungs. This distribution occurs as a result of its small and uniform particle size. Initial deposition into the lungs is monitored by placing a gamma camera over the lungs and having the subject inspire Technegas until a desired count rate for pulmonary imaging is achieved. Typically a subject may need to inhale Technegas for only a few breaths. If needed, the subject can take a rest breath (breathe normal air or oxygen) between Technegas inhalations.

The size distribution of Technegas delivered from the TechnegasPlus® Generator is well

controlled such that the median particle diameter size is 177 nm and ranges from 159-206 nm, and the ratio of the particle thickness to diameter is usually about 1:10.³

It is well established that particles smaller than 500 nm behave like true gases, distributing to the most peripheral regions of the lungs.⁴ Following distribution, Technegas particles do not pass through the alveolar membrane to enter the systemic circulation.^{5,6} Once deposited in the periphery of the lungs (below the level of the bronchociliary elevator), Technegas particles do not undergo diffusion, or exhibit other means of re-distribution, but are gradually cleared by lung macrophages.

Technegas particles initially deposited in the upper regions of the lung are removed by bronchociliary clearance and gastrointestinal elimination without absorption.³ Time-lapsed cinegraphic images of the chest region have documented that Technegas particles, initially deposited in the upper regions of the lung, are cleared by the bronchociliary elevator. The web site of The John Curtin School of Medical Research, Australian National University, includes a cinegraphic illustration of this clearance mechanism.⁷ The cine image illustrates the upward movement of the radioactive particles followed by swallowing, transit through the esophagus and delivery into the stomach.

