11.2.4 Oxygen Saturation of the Blood using Pulse Oximetry

Oxygen saturation of the blood using pulse oximetry will be collected within 30 minutes prior to the Xe-133 study. This will be considered the baseline measurement. Oxygen saturation will also be taken following completion of the Xe-133 imaging, but prior to Technegas imaging.

Oxygen saturation will be taken at approximately 10 minutes (\pm 5 minutes) prior to Technegas inhalation and within 15 minutes following completion of the Technegas imaging. Additional oxygen saturation will be taken during the 24-hour follow-up safety assessment.

The investigator will assess and comment if oxygen saturation falls below 90%.
Attributability of any changes below 90% will be assessed as follows:

- 1 = Attributable to disease; no follow-up required
- 2 = Attributable to Xe-133 procedure; no follow-up required
- 3 = Possibly attributable to Technegas, FOLLOW-UP REQUIRED

Any oxygen saturation measurements with clinically significant changes below 90% and possibly attributable to Technegas will be repeated at appropriate intervals following the procedure until the values return to baseline or until the investigator and the Medical Monitor agree that further follow-up is no longer clinically relevant.

Any changes considered clinically significant and assessed as “3 = Possibly attributable to Technegas, FOLLOW-UP REQUIRED” will be documented on the AE page of the CRF.

11.2.5 24-Hour Follow-Up Safety Assessment

Subjects will return to the clinical site for a 24-hour follow-up safety assessment, to occur within 20 to 36 hours following the Technegas procedure. Subjects will undergo a physical examination, a blood draw for clinical chemistry and hematology laboratory measurements, vital signs (systolic and diastolic blood pressure, pulse rate, respiratory rate), pulse oximetry, and adverse event and concomitant medication assessments. Adverse event follow-up safety assessment will conclude at this visit if none are noted.

Any changes that the investigator feels are clinically significant should be noted and the investigator will comment on whether the change can be attributed to Technegas. If clinically significant changes are noted, appropriate follow-up will be conducted by the investigator as long as deemed necessary.

Investigators will make every effort to obtain the 24-hour assessment, as agreed to by the subject prior to enrollment.

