13.8 Safety Endpoints

Safety endpoints include:

1. Incidence of treatment emergent AEs.
2. Changes (24 hours post-Technegas minus baseline) in laboratory measurements. The laboratory measurements at screening will serve as the baseline.
3. Incidence of clinically significant changes in laboratory measurements.
4. Change (post minus baseline) in vital signs at each time-point post Xe-133 and Technegas administration. The measurements within 30 minutes prior to Xe-133 inhalation will serve as the baseline.
5. Incidence of clinically significant changes in blood pressure (defined Section 11.2.3).
6. Change (post minus baseline) in oxygen saturation at each time-point post Xe-133 and Technegas administration. The measurements within 30 minutes prior to Xe-133 inhalation will serve as the baseline.
7. Incidence of treatment emergent abnormalities in physical examinations.

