13.9 Safety Analyses

The summary and analysis of safety data will be conducted on the modified ITT dataset.

Frequency distributions including counts and percentages will be used to summarize the qualitative safety data, including AEs, clinically significant changes in laboratory measurements and vital signs, and treatment emergent abnormalities in physical examinations. The summary of AEs will include summaries by MedDRA system organ class, relationship to study treatment, and event severity. Serious adverse events also will be summarized separately.

Summary statistics will be provided for all continuous safety data including change in laboratory measurements, vital signs and oxygen saturations. Paired t-tests will be used to test for statistically significant changes over time. The laboratory measurements at baseline and follow-up also will be categorized relative to their reference ranges as low, within range, or high, and shift tables comparing the distributions from baseline to follow-up will be provided for each test. The Stuart Maxwell test will be used to test for statistically significant changes in pre- versus post-treatment distributions.

14 Data Handling and Record Keeping

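### SpO2 is analysed only as change from baseline, with no count below the protocol's own 90% threshold and no record of air or oxygen at each reading

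*Combined protocol and SAP*

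**What the plan says.** The second primary objective (protocol section 5 and synopsis) is the safety profile of Technegas, and pulse oximetry is one of the measures it names.

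- **Readings.** Section 11.2.4 fixes the baseline: "Oxygen saturation of the blood using pulse oximetry will be collected within 30 minutes prior to the Xe-133 study". Further readings follow the Xe-133 imaging, then come about 10 minutes "prior to Technegas inhalation and within 15 minutes following completion of the Technegas imaging", and the last is at the 24-hour follow-up.
- **Threshold.** The same section states: "The investigator will assess and comment if oxygen saturation falls below 90" percent. The investigator then codes the cause. A clinically significant change coded as possibly due to Technegas goes on the adverse-event page.
- **Endpoint.** Section 13.8, item 6: "Change (post minus baseline) in oxygen saturation at each time-point post Xe-133 and Technegas administration". For blood pressure the list has a second, threshold-based entry: "Incidence of clinically significant changes in blood pressure (defined Section 11.2.3"). Laboratory values have a similar entry. Oxygen saturation does not.
- **Analysis.** Section 13.9 asks for summary statistics of the change and adds: "Paired t-tests will be used to test for statistically significant changes over time". The synopsis also allows the signed rank test.
- **Oxygen.** Section 4.1, repeated in section 4.5: "If needed, the subject can take a rest breath (breathe normal air or oxygen) between Technegas inhalations".

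**The concern.** Breathing oxygen raises the quantity that the endpoint measures. If a subject's oxygen use differs between the baseline and a later reading, the change score mixes two things: what happened to oxygenation, and what gas the subject was breathing. The plan permits oxygen around the inhalation and does not ask for it to be noted beside the reading.

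Separately, desaturation is a concern about individual subjects. The protocol recognises this by setting a 90% rule, then analyses only the change on a continuous scale. A reader of the safety tables would not find how many subjects were below 90% at any time, or how many were newly so. What is at stake is whether a measure named in a primary objective can be interpreted. The efficacy analysis is not affected.

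**Working it through.** No figure in the documents depends on this point, so there is none to reproduce. The check is mainly a comparison of sections.

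**1. Endpoints side by side (section 13.8)**

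| Measure | Rule for a notable value | Change endpoint | Incidence endpoint |
|---|---|---|---|
| Laboratory values | investigator judgement (11.2.1) | item 2 | item 3 |
| Blood pressure | change above 45 mm Hg systolic or 30 mm Hg diastolic (11.2.3) | item 4 | item 5 |
| Oxygen saturation | below 90% (11.2.4) | item 6 | none |

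The asymmetry is plain from the text and needs no assumption.

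**2. Where oxygen use could be captured**

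- Section 9.2 lists the inhalation data for the CRF: the number of inhalations and the times of the first and last. Oxygen is not among them.
- Section 11.2.4 and the schedule in section 12.3 do not ask what gas was being breathed at a reading.
- Section 8.2 requires all medications on the CRF, with total daily dose, route and dates. It does not name oxygen and asks for no clock time. Four of the five readings belong to the imaging visit, normally a single date, so a dated entry cannot be placed before or after any one of them.
- Section 11.5 records treatment given for an adverse event, but only once an event has been reported.

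**3. What the change score then contains**

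Recorded change = change on the same inspired gas + effect of any change in inspired gas.

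Without oxygen status the two terms cannot be separated. Air at baseline and oxygen later can hide a fall. Oxygen at baseline and air later can create one. The 90% comment acts on the value read, so a reading of 90% or more taken on oxygen does not trigger it.

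**4. Illustration on assumed values**

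Only N = 240 comes from the protocol (section 13.6). Assume a share f of subjects falls by D points, a share m of those is back at baseline by the reading, and all other changes have mean 0 and SD 2 points.

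- Mean change = -f × D × (1 - m)
- SD = √(2² + f(1 - m)D² - mean²)
- z = mean / (SD/√240)

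| f (subjects) | D | m | Mean change | z |
|---|---|---|---|---|
| 2% (5) | 4 | 0 | -0.08 | -0.60 |
| 2% (5) | 8 | 0 | -0.16 | -1.08 |
| 5% (12) | 8 | 0 | -0.40 | -2.34 |
| 5% (12) | 8 | 0.5 | -0.20 | -1.31 |
| 10% (24) | 8 | 0 | -0.80 | -3.97 |
| any | any | 1 | 0.00 | 0.00 |

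Two things follow. Even when every fall is recorded in full (m = 0), five subjects falling by 8 points barely move the mean, which is the case for an incidence row. And when m is unknown, the same mean change is compatible with different histories. The rows with m above 0 apply equally to recovery without oxygen, so they are not evidence that oxygen causes a bias.

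**5. How much new data a CRF field would bring**

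The SAP addendum, section 2, reports 209 subjects complete against a target of 240. At most about 240 - 209 = 31 subjects, or 31/240 = 12.9% of the target, would have the field completed prospectively.

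**The case against.** The strongest reply is that endpoint 6 is not the only safety output on oxygenation, and this stands. Section 11.2 makes a clinically significant worsening of any safety parameter an adverse event. Section 11.2.4 sends falls possibly due to Technegas to the adverse-event page. Section 11.5 records deterioration in clinical findings and any treatment given for it. Adverse events are monitored throughout, not only at the reading times. Section 13.1 adds the minimum, the maximum and individual listings, so an extreme recorded change would be visible and every recorded reading below 90% would be listed. What these routes do not give is a planned count below 90%, or the oxygen status of a reading.

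A reader might infer something stronger: that oxygen is given to subjects who desaturate, is still running at the post-imaging reading, and so biases the result toward no effect. The documents do not support that. They offer oxygen as an optional rest breath, with normal air as the alternative, in background sections. The operative procedure in section 9.2 does not mention it. Nothing says that it treats a fall or continues after imaging. No reading is scheduled during inhalation, so a brief fall that recovers unaided would be missed in the same way.

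It would also be too strong to say that oxygen is never recorded. Section 8.2 may capture it, and the CRF, Imaging Manual and SAP Version 2 were not among the documents supplied.

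**Conclusion.** The point holds as a gap in one safety endpoint. Oxygen saturation has no incidence endpoint for the protocol's own 90% threshold, and its change score cannot be read apart from oxygen use. The first part rests on the text of sections 11.2.4 and 13.8 alone. The second rests on the supplied sections being complete on what is recorded, which the CRF or SAP Version 2 could alter.

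The size cannot be derived from the documents. They do not say how often subjects fall, by how much, or how often oxygen is used. The mean changes of -0.08 to -0.80 points shown with no correction come from assumed shares of 2% to 10% and assumed falls of 4 to 8 points; they are illustrations, not estimates. Neither a directional bias nor a hidden safety signal is established. The change is worth making because it is cheap and concerns a measure named in a primary objective.

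**What to change.** 1. In sections 13.8 and 13.9, add the number and percent of subjects with SpO2 below 90% at each time point, and among them the number newly below 90% relative to baseline. This uses readings already collected and can cover all subjects.
2. Record room air or supplemental oxygen at each existing SpO2 reading: prospectively for subjects still to be enrolled, and from source records where available for completed subjects.
3. Show SpO2 change separately for subjects whose oxygen status did and did not change between baseline and the reading, with a third group where status is unknown.

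A composite that treats any newly started oxygen as an event is not advisable, because it would count a permitted rest breath as an oxygenation problem. No change to care or to the reading times is proposed.

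The cost is a small CRF addition at the five existing time points and a few table rows. Oxygen status will be incomplete for the 209 subjects already finished, so item 3 may be sparse. The SpO2 table may also look slightly less favourable. Item 1 carries no data-collection cost and should go ahead even if items 2 and 3 prove impractical.

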13.9 Safety Analyses

The summary and analysis of safety data will be conducted on the modified ITT dataset.

Frequency distributions including counts and percentages will be used to summarize the qualitative safety data, including AEs, clinically significant changes in laboratory measurements and vital signs, and treatment emergent abnormalities in physical examinations. The summary of AEs will include summaries by MedDRA system organ class, relationship to study treatment, and event severity. Serious adverse events also will be summarized separately.

Summary statistics will be provided for all continuous safety data including change in laboratory measurements, vital signs and oxygen saturations. Paired t-tests will be used to test for statistically significant changes over time. The laboratory measurements at baseline and follow-up also will be categorized relative to their reference ranges as low, within range, or high, and shift tables comparing the distributions from baseline to follow-up will be provided for each test. The Stuart Maxwell test will be used to test for statistically significant changes in pre- versus post-treatment distributions.

14 Data Handling and Record Keeping

14.1 Case Report Forms

Electronic CRFs (eCRFs) will be used and clinical trial data will be entered directly into the electronic data capture (EDC) system. The EDC system will be a 21 Code of Federal Regulations (CFR) Part 11 compliant data capture system. The data system will include password protection, logs to identify individual entering or correcting data and internal quality checks, such as automatic range checks, to identify data that appear inconsistent, incomplete, or inaccurate. Any changes, corrections or deletions made in the eCRFs will identify the responsible investigator or other authorized person modifying the data. The investigator will review the completed eCRFs and electronically sign and date them to indicate his/her review, agreement with the data included, and the completeness and accuracy of the data.

Case report forms (CRFs) must be completed for all enrolled subjects, even if the subject fails to complete the study. No section of the CRF is to be left blank without an appropriate explanation by the investigator, since the lack of such explanation may necessitate discarding an otherwise usable observation.

14.2 Completing, Signing and Archiving Case Report Forms

Data collection is the responsibility of the investigator at the investigative site or clinical trial staff under the supervision of the respective site investigator. The investigator is responsible for ensuring the accuracy, completeness, legibility, timeliness and attributability of the data reported.

Clinical data may be entered directly into the eCRF at the time of data collection or from the source documents. Data reported in the eCRF derived from source documents should be consistent with the source documents or the discrepancies should be explained and captured in a study note and maintained in the participant's electronic study record.

To comply with the requirement to maintain accurate case histories investigator(s) should review and electronically sign the completed eCRF for each subject before the data are archived or submitted to FDA. If changes are made to the eCRF after the investigator(s) has already signed, the changes should be reviewed and electronically signed by the clinical investigator(s).

14.2.1 Archiving of Records

The following information must be retained at the investigational site for at least 2 years after the last approval of a marketing application and until there are no pending or contemplated marketing applications in an ICH region; or until at least 2 years have elapsed since the

formal discontinuation of clinical development of the investigational drug; or for the maximum period of time as required by the study center, whichever is greater:

- Source data (including digital images)
- Source documents
- Copies of protocols
- Protocol amendments
- Correspondence
- Subject identification codes and lists
- Signed informed consent forms
- Any other essential documents pertaining to the conduct of the study

No study document or image should be destroyed without prior written agreement between the sponsor and the investigator(s). Should the investigator(s) wish to assign the study records to another party or move them to another location, advance written notice should be given to the sponsor.

It is the responsibility of the sponsor to inform the investigator(s)/institution(s) when these documents need no longer be retained.

The sponsor will ensure all other study documents (e.g.: protocol, report, all data management documentation) are filed and archived in a secure area in the Trial Master File for at least 2 years after the last approval of a marketing application and until there are no pending or contemplated marketing applications in an ICH region; or until at least 2 years have elapsed since the formal discontinuation of clinical development of the investigational product; or for the lifetime of the product, as required by regulation. In addition, the final trial report must be retained by the sponsor, or the subsequent owner, for five years beyond the lifetime of the study agent.

14.3 Direct Access to Source Data/Documents

All information in original records and certified copies of original records of clinical findings, observations, or other activities in a clinical trial necessary for the reconstruction and evaluation of the trial will be made directly available for clinical monitoring activities. Source data are contained in source documents (original records or certified copies). Source documents are original documents, data, and records (e.g. hospital records, clinical and office charts, laboratory notes, memoranda, subjects' diaries or evaluation checklists, pharmacy dispensing records, recorded data from automated instruments, copies or transcriptions certified after verification as being accurate and complete, microfiches, photographic

negative, microfilm or magnetic media, x-rays, subject files, and records kept at the pharmacy, at the laboratories, and at medico-technical departments involved in the clinical trial).¹³

All source documents must be accurate, clear, unambiguous, legible, contemporaneous, original, permanent and available for inspection and audit. Paper-based source documents should be made using a permanent form of recording (ink, typing, printing, optical disc, etc.) and they should not be obscured by correcting fluid or have temporary attachments (such as “post-it” notes).

If electronic medical records are used as source data to support trial data, the investigator will authorize the monitor to compare the data stored in the electronic medical records to the CRF data to ensure all data are complete, consistent, and accurate and ensure prior to enrolling a subject that a GCP-compliant method of doing this is available for the monitor.

If electronic medical records are used to support trial data and the monitor is not allowed direct access to the electronic medical records for monitoring and data verification purposes, the source documents that are computer-generated and stored on magnetic support media must be printed and must be certified by the investigator as being an exact duplicate of the original electronic record. The investigator or designee will identify each printed page as a certified copy and will sign and date the printed pages to so indicate.

The minimum requirements for source documents used in clinical trials are that they should contain: the identity of the subject (or trial-related identifiers such as trial enrollment number, treatment number), the subject’s participation in the trial (protocol/study title or number), subject’s demographic data, the date and time the subject provided informed consent, the subject’s medical history, the treatment that the subject received, AEs, SAEs and the dates of the trial visits. The end of the subject’s trial participation must be documented. Information recorded in the CRF must be consistent with entries in the source documents.

The following data may be recorded directly in the CRF. If it is, it will be considered as source data:

- Imaging parameters
- Assessment of images for technical adequacy

If other data are recorded directly into the CRF at the time the data are obtained, it will be considered as source data, too. The investigator must document in the study file the use of the CRF as its own source document for any such data.

Source documents in connection with the study, including but not limited to, subject charts, radiology reports and laboratory data, will be made available to the sponsor upon request with due precaution towards protecting the privacy of the subject.

